From mothers, we will collect self-report responses about their background sociodemographic factors, including use of other pregnancy/parenting/infant care resources, and their perceptions about fathers' caregiver conflict, and about their infant, as well as their perceptions of father's parenting and infant care self-efficacy, cooperative coparenting, relationship quality, and partner behavioral engagement in

infant care, using a shorter survey instrument at baseline and 2 months of postnatal age (7-month follow-up) in-person, via phone, or electronically via Qualtrics. This shorter survey takes about 15-20 minutes to complete.

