## 5. Inclusion/Exclusion Criteria

Inclusion criteria: In order to be eligible to participate in this study, an individual must meet all of the following criteria:

1. Provision of signed and dated informed consent form
2. Stated willingness to comply with all study procedures and availability for the duration of the study
3. Self-reported expectant father and pregnant partner (expectant mother)
4. Aged  $\geq 18$  years
5. In a romantic relationship and expect to continue to be in this relationship during the study period
6. Willingness to adhere to the Text4Father regimen (for fathers)
7. English speakers only: The Text4Father content was not developed for use with non-English speakers or hearing-impaired individuals. Therefore, non-English speakers and hearing-impaired individuals will not be included.
8. Lower socioeconomic status (SES) (e.g., less than a 4-year college degree, or vocational/trade school or less, or qualify for Medicaid/public insurance)
9. Access to necessary resources for participating in a technology-based intervention (i.e., cell phone) and willing/able to receive/send texts

Exclusion criteria: An individual who meets any of the following criteria will be excluded from participation in this study:

1. Individuals who are not able to provide informed consent.

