## 7. Study Statistics

Name	Parenting Sense of Competence (PSOC)
Type	Primary
Time Frame	Baseline; post-treatment at follow-up
Brief Description	Measures parents' perceived confidence (self-efficacy) with overall parenting and parenting skills

Name	Technology usability
Type	Other
Time Frame	Post-treatment at follow-up
Brief Description	Assesses technology usability among participants assigned to the intervention
Name	Technology acceptance
Type	Other
Time Frame	Post-treatment at follow-up
Brief Description	Assesses technology acceptance among participants assigned to the intervention

a. Statistical plan including sample size justification and interim data analysis.

**Number of subjects expected to enroll:** Total of N=240 (120 fathers; 120 mothers) or 60 couples per group (treatment, and standard of care control).

**Expected effect size:** Moderate effect size (i.e.,  $d \geq 0.472$ ).

**Power.** We evaluated power for the fixed effects in a hierarchical linear model including four discrete covariates to consider the average rate of change in paternal parenting constructs due to the intervention over duration of the study time period. With a sample size of N=60 participants per study arm, we will have 80% power to detect moderate effect size (i.e.,  $d \geq 0.472$ ) in outcomes. This power calculation also accounts for study attrition (anticipated at 20% loss to follow-up over the 7-month study period). We used one of the few studies that evaluated changes in parenting constructs comparing treatment for father engagement to a control group only at the end of treatment to inform these calculations and expected effect size. This study found treatment fathers had 12.7% higher paternal infant engagement at the end of the treatment compared to the control group; and parenting self-efficacy was 6.2% higher in treatment than in control group participants.

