### Statistical methods

**Aims 1 and 2. Feasibility and Acceptability.** Using completed clinic appointment, screener, and consent data, we will assess feasibility of overall recruitment by calculating the proportion of eligible fathers who consent to study participation and recruitment by resident status. Based on our pilot work, we anticipate recruiting  $\geq 70\%$  of fathers who are approached. We will calculate feasibility of retention as the proportion of enrolled participants who complete 7-month follow-up survey (2-months of postnatal age). We will calculate study retention overall and separately by treatment assignment and use Chi-square tests to determine if we achieved follow-up of  $\geq 80\%$  by treatment assignment.

In the Text4Father arm, we will calculate the proportion of individuals completing the

intervention and assess at exit these participants' technology usability (12 items), acceptance (8 items), and satisfaction (1 item) (on 5-point scales from "strongly disagree" to "strongly agree"). We will examine whether we achieved  $\geq 75\%$  agree/strongly agree usability/acceptability rates and generate means (SD) for each.

**Aim 3. Efficacy.** We will examine the effect of the randomization scheme and explore missing data due to survey non-response and attrition. We will then apply separate random intercept coefficient regression models for each study outcome accounting for two levels of nesting (repeated measures and individuals). Each model will estimate differences among intervention and usual care control arms identifying change in each study outcome between baseline and follow-up. This type of analysis will allow for examining 1) within-individual change over time in an outcome, accounting for dependency among observations within individuals by modeling within-person error, 2) between-individual variation over time, and 3) between-subjects effects based on group assignment to identify significant differences in content (Text4Father) as compared to usual care. Our sample size should be large enough to adequately power analyses for examining change in fathers' engagement (see below). The fixed effects from these analyses will help determine the expected effect size for other outcomes to inform power calculations for a larger R01-funded trial.

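### Aim 3 names no missing-data method and does not use mother-reported relationship and outcome data that could reduce, though not remove, a possible bias from fathers lost to follow-up

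*Combined protocol and SAP*

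**What the plan says.** Section 7, Statistical methods, Aim 3 disposes of missing data in one sentence: "We will examine the effect of the randomization scheme and explore missing data due to survey non-response and attrition". It states no assumption, imputation method, auxiliary variable or sensitivity analysis. The analysis that follows is "separate random intercept coefficient regression models for each study outcome accounting for two levels of nesting (repeated measures and individuals"), with no couple level and no partner data. Covariates appear only in the Power paragraph, which refers to a "hierarchical linear model including four discrete covariates" and does not name them.

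Loss is "anticipated at 20% loss to follow-up over the 7-month study period". Section 4, Participants and Recruitment, sets 60 dyads per arm so that 48 are complete. Fathers have two surveys, at baseline and at the 7-month follow-up (2 months after birth).

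Section 5 requires every participant to be "In a romantic relationship and expect to continue to be in this relationship during the study period", so any break-up happens after baseline.

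The mother's survey, given at the same two time points, includes "cooperative coparenting, relationship quality, and partner behavioral engagement". The Measures Table marks six outcomes as reported by both parents: parenting self-efficacy, infant care self-efficacy, cooperative coparenting, partner relationship quality, infant engagement and time with the infant. Section 8b sends interval texts to all mothers, asking whether the relationship is better, the same or worse. In the analysis plan, relationship variables serve as outcomes and as exploratory moderators, not in handling missing data.

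**The concern.** With one follow-up, a likelihood fit of the planned model in effect predicts a lost father's outcome from his arm, his own baseline and any covariates. Change in the relationship after baseline is not among these, unless one of the four unnamed covariates measures it, and nothing suggests that. Section 7 (Exploring moderating factors) accepts that residence, relationship quality and conflict may affect a father's access to and engagement with the infant. It is a reasonable judgement that the same events make a father harder to reach.

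There are also reasons why loss could work differently by arm. Text4Father fathers get about two texts a week, while usual care gets three interim texts. The removal rule in section 4f starts from a platform error on a dead number, so it depends on texts being sent. Section 8a allows that the intervention could increase friction between caregivers. Retention will be reported by arm, but nothing in the analysis follows from it.

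At stake are the effect sizes that this study is meant to supply to a larger trial.

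**Working it through.** **The plan's own figures.** 48 / (1 − 0.20) = 60, so the enrolment figure reproduces. The power statement is "With a sample size of N=60 participants per study arm, we will have 80% power to detect moderate effect size", for d = 0.472 with attrition allowed for. Alpha is not given. At two-sided 0.05, without covariate adjustment and by normal approximation, 48 per arm gives 63.8% and 60 per arm gives 73.4%. At 48 per arm the effect detectable with 80% power is 0.572, and (0.472 / 0.572)² = 0.681. Setting 1 − ρ² = 0.681 gives a baseline–follow-up correlation of about 0.56 (baseline adjustment); setting 2(1 − ρ) = 0.681 gives about 0.66 (change score). So 80% is reachable with a correlation that the plan does not state. Nothing below depends on this.

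**Bias when the father's own baseline is the only predictor.** From the plan: 20% loss (taken as equal in both arms) and d = 0.472. Assumed: a share p of couples break up, independently of the baseline score; the outcome is then δ SD lower; fathers are lost with probability q after a break-up. Among observed fathers the share with a break-up is p(1 − q) / 0.80. The arm mean is therefore too high by

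δ × [p − p(1 − q) / 0.80].

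| p | q | Share among observed | Bias in arm mean | δ range | Result (SD) |
|---|---|---|---|---|---|
| 0.20 | 0.50 | 0.125 | 0.075δ | 0.5–1.0 | 0.04–0.075 |
| 0.20 | 0.60 | 0.100 | 0.100δ | 0.5–1.0 | 0.05–0.10 |
| 0.15 | 0.60 | 0.075 | 0.075δ | 1.0–1.5 | 0.075–0.11 |
| 0.25 | 0.60 | 0.125 | 0.125δ | 1.0–1.5 | 0.125–0.19 |
| any | 0.20 | p | 0 | any | 0 |

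For the arm difference:

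- Same p and q in both arms: the two biases cancel, and the difference is unbiased.
- Break-up raises loss in one arm only (q = 0.20 in the other): the difference is off by the tabulated amount. If the affected arm is usual care, the effect is understated; at most, 0.472 − 0.1875 = 0.285. If it is Text4Father, the effect is overstated by the same amount.
- Break-up is 25% in one arm and 15% in the other, with q = 0.50 in both: (0.09375 − 0.05625)δ = 0.0375δ, or 0.02–0.04 SD for δ of 0.5–1.0.

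**What the mother's report recovers.** Take p = 0.20 and q = 0.50, so that loss without break-up is (0.20 − 0.10) / 0.80 = 0.125. Suppose her report of a break-up has 80% sensitivity and 90% specificity (assumed).

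- Report positive: observed fathers 0.08 with and 0.07 without break-up, so the imputed share is 0.08 / 0.15 = 0.533; lost fathers 0.09.
- Report negative: observed 0.02 and 0.63, so the imputed share is 0.02 / 0.65 = 0.031; lost fathers 0.11.
- Break-ups imputed among the lost: 0.09 × 0.533 + 0.11 × 0.031 = 0.051. The truth is 0.20 × 0.50 = 0.100. Using the father's baseline alone gives 0.20 × 0.125 = 0.025.
- Share of bias removed: (0.051 − 0.025) / (0.100 − 0.025) = about 35%.

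This shrinks in proportion to the lost fathers whose partners report. If 10% of mothers are missing, it is 0.9 × 35% = 32%. If half of lost fathers' partners are also lost and 10% of the rest are missing, it is 0.45 × 35% = 16%. If 80% are also lost, it is 0.18 × 35% = 6%. Large-sample simulation agrees (about one third, 15%, and 5–8%). A perfect and complete report brings the bias to zero.

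If loss depends instead on the father's own unseen outcome in usual care only (logit slope −1 per SD), simulation gives 0.34 with the father's baseline alone. Adding the mother's report of the same outcome gives 0.351–0.376 (father–mother correlation 0.4–0.6). That recovers 0.011 / 0.132 = 8% to 0.036 / 0.132 = 27% of the gap to 0.472.

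**The case against.** The strongest reply is that no bias has been demonstrated. No passage links break-up to loss, the break-up and loss rates are invented, and the larger figures require break-up to drive loss in one arm and not at all in the other. All of this stands. A reader might infer that the planned analysis is biased, that it understates the effect, and that the trial holds the data to correct it. The documents support none of the three: differential loss is possible but not established, its direction is unknown, and the correction is partial.

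Second, the sample is small. At p of 0.15–0.25 and q = 0.60, only 60 × p × 0.40 = 3.6 to 6 separated fathers in an arm would be observed, and the SD of the estimate is about 0.21–0.23, larger than any bias shown. This stands as a reason for a short auxiliary set. It does not favour the father-only model: in re-runs at 60 per arm, adding the mother's report left the SD almost unchanged and did no harm when the mechanism was equal in both arms.

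Third, coverage is incomplete. Mothers report on three of the six primary outcomes; knowledge, role beliefs and attachment beliefs are father-only. The plan counts completeness by dyad, so couples may well be lost together. A follow-up record of relationship status is also not secure: the Measures Table lists it as a background factor, the Schedule of Activities marks background items at Visit 1 only, and the Surveys text can be read as collecting them at both visits. Relationship quality at follow-up and the interim texts do not depend on that reading.

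Finally, this is a preliminary-efficacy study that already reports retention by arm and pays participants to limit loss. That lowers the urgency, but the effect estimates are still the intended product.

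**Conclusion.** The point holds in a limited form. Aim 3 specifies no missing-data method, its models rest on loss being at random given arm, the father's own baseline and any covariates, and mother-reported follow-up data that could make this more plausible go unused for lost fathers. The bias in the arm difference is zero if the loss mechanism is the same in both arms. In the scenarios examined it is otherwise up to about 0.19 SD, in either direction. These figures are illustrative: only the 20% loss and the 0.472 come from the plan. The maternal data would reduce such a bias by an amount that depends on how accurate her report is and how often both partners are lost. This is an available improvement at low cost, not proof that the planned result would be wrong.

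**What to change.** In Aim 3, pre-specify multiple imputation (or a joint model) of missing follow-up father outcomes, by arm, with a short auxiliary set:

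- the father's baseline score and resident status;
- the mother's follow-up report of the same outcome, for the six outcomes where one exists;
- her follow-up relationship quality;
- her interim-text answers about the relationship.

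Add her follow-up relationship status only if the Schedule of Activities and the Surveys text are reconciled to show that it is collected.

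Always report this estimate beside the father-only model. Do not make its standing depend on whether observed retention differs by arm. The bias shown above arises with equal 20% loss in both arms, and a choice made after seeing retention is data-dependent.

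Reconcile the passages on interim queries. Control Groups and section 4b include the usual care arm, while section 8b describes queries to all mothers but only to intervention fathers. The mothers' texts are the one stream described consistently for both arms.

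**Cost.** Analysis wording and modest programming, with no new data collection. State the limits: the auxiliary set must stay small because only about 48 fathers per arm are expected to complete; the benefit is partial when her report is imprecise; only the interim texts remain when both partners are lost; and knowledge, role beliefs and attachment beliefs can draw only on relationship data.

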**Exploring moderating factors.** We will explore the moderating effect of fathers' resident status, partner relationship quality, and caregiver conflict from perspectives of both parents on the study's outcomes given that each of these may influence fathers' access and experience with infant engagement, as well as other background factors. These findings will inform sampling decisions and future research questions for a larger trial. We will also explore how infant sex as a biological variable might impact father engagement; however, this is not supported by past work in this area.

We will also explore differences among intervention and usual care control arms for each maternal and infant outcome between baseline and follow-up.

b. Early stopping rules.

This study may be stopped prior to its completion if:

- (1) participants experience (adverse events) AEs or severe AEs (SAEs) that are felt to be related to study participation, at which point consideration will be given to temporarily or permanently suspending study activities and/or enrollment. This decision would be made in consultation with the study's IRB and sponsor (NICHD);
- (2) difficulty in study recruitment or retention will significantly impact the ability to evaluate the study endpoints. The investigators will consult with the study monitors to assess the impact of significant data loss due to problems in recruitment, retention, or data collection;
- (3) any new information becomes available during the trial that necessitates stopping the trial; or
- (4) other situations occur that might warrant stopping the trial.

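### The Aim 3 change model is applied to every outcome, but at least two infant-care behaviours have no baseline value before birth; outcomes measured twice would gain precision from baseline adjustment

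*Combined protocol and SAP*

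**What the plan says.** Section 7, Statistical methods, Aim 3 gives one model for all outcomes: "We will then apply separate random intercept coefficient regression models for each study outcome accounting for two levels of nesting (repeated measures and individuals"). Every such model is described as "identifying change in each study outcome between baseline and follow-up", and no outcome is exempted. The same paragraph lists "between-subjects effects based on group assignment" among the things the analysis can examine. It says the sample should "adequately power analyses for examining change in" fathers' engagement, and that the fixed effects will serve "to inform power calculations for a larger R01-funded trial". Under Exploring moderating factors, arm differences are to be explored "for each maternal and infant outcome between baseline and follow-up".

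The power paragraph of Section 7 rests on a "hierarchical linear model including four discrete covariates". Aim 3 names no covariates. The effect-size source cited there compared arms only at the end of treatment.

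On timing, Section 4 (Participants and Recruitment) enrols through 25 weeks of gestation. The Randomization Schedule paragraph places the baseline survey before assignment. Follow-up is at 2 months of postnatal age. The Measures Table lists five secondary outcomes: partner relationship quality, infant engagement, time spent with the infant, safe sleep care and injury prevention care. The Conceptual Framework text in Section 4 places the behavioural ones at follow-up. For parenting self-efficacy, the outcome table in Section 7 gives the time frame "Baseline; post-treatment at follow-up".

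**The concern.** A change model needs two measurements of the same quantity. At baseline the study infant is unborn, so days and hours spent with that infant, and engagement in caring for that infant, do not yet exist. Involvement in the pregnancy is a different quantity and cannot stand in for them. The plan nevertheless describes change in fathers' engagement as the effect it is sized to examine, and intends to carry the fixed effects forward to a larger trial. Generating effect sizes is part of the primary objective, so the quantity to be reported should be defined.

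A second, smaller matter concerns outcomes measured at both visits, including the six primary ones. The model equation is not written out. If baseline means are left free in each arm, the baseline scores already collected are used less efficiently than they could be.

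**Working it through.** **1. The plan's own figure.** Stated: 60 per arm, 20% attrition, 80% power at d = 0.472. The attrition step reproduces: 48 / (1 − 0.20) = 60. Neither alpha, sidedness, the baseline-to-follow-up correlation (rho) nor the covariates' R² is stated. Taking two-sided alpha 0.05 and d in follow-up SD units, power = Φ(0.472 / √(2/n) − 1.96), which is 63.8% at n = 48 and 73.4% at n = 60. To reach 80% with 48 per arm needs one of: covariate R² of about 0.32, baseline adjustment with rho of about 0.56, or a change score with rho of about 0.66. The 80% is therefore not reproducible from the printed inputs, but it is not shown to be wrong.

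**2. Outcomes with a single post-birth record.** Write the fixed effects as intercept, arm, time and arm-by-time. If time = 1 for every record, the time column equals the intercept and the arm-by-time column equals arm. The design has rank 2 of 4, so change is not estimable. Each record has variance (intercept variance + residual variance), and only the sum is identified. In 96 simulated fathers (48 per arm), five different splits of the same total gave identical results: arm contrast 0.480638, SE 0.204124 (= √(2/48)), log-likelihood −123.4664. The 2-month contrast is thus well defined, while the change effect and the variance split are not.

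**3. Which outcomes are affected.**

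| Secondary outcome | Reporter | Study-infant value at baseline? |
|---|---|---|
| Infant engagement | father, mother | No |
| Time spent with infant | father, mother | No |
| Safe sleep care | father | Cannot be told; items not printed |
| Injury prevention care | father | Cannot be told; items not printed |
| Partner relationship quality | father, mother | Yes; a Time 1 value is listed as a moderator |

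**4. Outcomes measured twice.** Assumptions: two-sided alpha 0.05, SD 1 at both visits, 60 baseline and 48 follow-up records per arm, dropout at random. Variance per arm:

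- baseline means free by arm: (1 − rho²)/48 + (1 − rho)²/60
- adjusted for baseline: (1 − rho²)/48

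SE = √(2 × variance per arm); power = Φ(0.472/SE − 1.96); detectable d at 80% power = 2.80 × SE.

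| rho | Variance, free | Variance, adjusted | Ratio | Power, free → adjusted | Detectable d |
|---|---|---|---|---|---|
| 0.3 | 0.02713 | 0.01896 | 0.70 | 53% → 68% | 0.65 → 0.55 |
| 0.5 | 0.01979 | 0.01563 | 0.79 | 66% → 76% | 0.56 → 0.50 |
| 0.7 | 0.01213 | 0.01063 | 0.88 | 86% → 90% | 0.44 → 0.41 |

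Simulation (20,000 trials per rho, adjustment slope estimated) gave ratios 0.703 / 0.795 / 0.883. The estimators averaged 0.47 against a true 0.472, so neither is biased.

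**5. A mixed model with equal baseline means.** This recovers the same gain when the two visits have equal SDs. A random-intercept model forces equal variances, and that matters if they differ. Let the follow-up SD be 1, the baseline SD s, and the pooled variance v = (s² + 1)/2. The model's implied slope on baseline is rho·s/v. The variance it claims, v(1 − slope²), is v times the true variance of the estimate, whatever rho is. The type I error of a nominal 5% test is then 2 × [1 − Φ(1.96√v)]:

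- s = 0.6: v = 0.68, type I error 10.6%
- s = 1.5: v = 1.625, type I error 1.2%

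Simulated null trials agree (about 11% and 1.4%), against about 5% for regression on the baseline score. The SD ratios are assumptions. Unequal spread is plausible, for instance because the attachment measure covers both fetal and infant attachment.

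**The case against.** The strongest reply is that the intent can be inferred. The Conceptual Framework already places these behaviours at follow-up, Aim 3 mentions between-subjects effects, and with one record per father any software reduces to a two-group comparison. No biased estimate follows. These are secondary outcomes of a preliminary-efficacy study, and the maternal analyses are exploratory. All of this stands, and it limits the severity. It does not remove the gap: Aim 3 says each model identifies change, and nowhere names the 2-month contrast or its covariates for these outcomes.

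A second reply is that Table 1 and the Surveys text list behaviour content at baseline for both parents. That is so, and the absence of a baseline value is inferred from timing rather than stated. But no baseline item can measure time with an infant not yet born, so those sections need clarifying.

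A reader might infer that most of the secondary outcomes are affected. The documents establish only two of five. Some safe-sleep or injury items, such as preparing the home, could be answered before birth.

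A reader might also take 63.8% as the power lost through this problem. It is the power of any unadjusted 48 v 48 comparison at d = 0.472 and does not measure the defect. The four planned covariates may already recover some of the difference from 80%.

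**Conclusion.** The point holds in limited form. For infant engagement and time with the infant, as reported by either parent, the stated change effect cannot be estimated and the random intercept is not identifiable. The 2-month difference between arms is estimable, and it matches both the Conceptual Framework and the end-of-treatment source of the effect size. The defect is a mismatch between sections, with no numerical cost that the documents allow one to state.

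The precision gain for outcomes measured twice is conditional. It applies only if Aim 3 means an arm-by-time model with free baseline means, and its size (variance ratio 0.70 to 0.88) rests on assumed correlations of 0.3 to 0.7 and equal SDs at the two visits. If baseline means are already constrained equal under a suitable covariance, there is nothing to gain. It would be wrong to conclude that the primary analyses are biased or invalid. Severity is minor to should-fix.

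**What to change.** 1. **Post-birth behaviours.** In Aim 3, and for the mother-reported versions under Exploring moderating factors, state that infant engagement, time spent with the infant, and any safe-sleep or injury item needing a born infant will be compared between arms at 2 months. Use regression on arm plus prespecified baseline covariates already collected (resident status and Time 1 partner relationship quality are candidates), with no change score or random intercept. List the covariates and say whether they are the four in the power paragraph. Reword the sentence on change in fathers' engagement as a 2-month difference.
2. **Baseline content.** In Table 1 and the Surveys text of Section 4, state measure by measure what is asked of each parent at baseline.
3. **Outcomes measured twice, including the six primary outcomes.** Write out the equation: follow-up score on arm plus baseline score. A mixed model with baseline means constrained equal is acceptable only with an unstructured covariance, giving each visit its own variance.

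The cost is a few sentences of text. No added data, visits or participants are required.
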